**STUDY SUMMARY:**

Investigational Agent(s) (Drugs or Devices)	Lidocaine 2%
IND / IDE / HDE #	NA
Indicate Special Population(s)	NA
Sample Size	20
Funding Source	Internal
Indicate the type of consent to be obtained	Written
Site	Single
Research Related Radiation Exposure	Yes
DSMB / DMC / IDMC	No

**OBJECTIVES:**

Participants with chronic, refractory phantom limb pain (PLP) or residual limb pain (RLP) for more than 6 months will be enrolled in this clinical trial.

Aim: Define the attributable pain relief and functional improvement in participants with PLP/RLP after contralateral limb sciatic nerve block. Also, contribute to the basic science understanding of the crossed-withdraw reflex by demonstrating a known animal model phenomenon in human participants.

Hypothesis: Contralateral limb sciatic nerve anesthetic block with 2% lidocaine provides immediate clinically meaningful pain reduction, defined as the proportion of patients with at least 50% improvement in NRS pain score in PLP/RLP when compared to sham.

**BACKGROUND:**

RLP and PLP affect most amputees at some point in their life. The incidence of PLP has been estimated to range between 50 – 80%. The prevalence of RLP has been estimated to be approximately 40%. RLP is more common in the first year after amputation, with PLP becoming the predominate amputee pain complaint after one-year post-amputation.

Both RLP and PLP fall under the umbrella term “post-amputation pain.” While these conditions are frequently found in combination, their clinical features are distinct and may share a common pathophysiological mechanism with neuroma formation. PLP is a painful sensation in the distribution of the missing limb. Following amputation, abnormalities at multiple levels of the neural axis have been implicated in the development of PLP; changes include cortical reorganization, reduced inhibitory processes at the spinal cord, synaptic response changes and hyperexcitability at the dorsal root ganglion, retrograde peripheral nerve shrinkage, and neuroma formation.

RLP may be caused by a number of conditions, including skin pathologies (i.e. stump edema, verrucose hyperplasia, epidermoid inclusion cysts, contact dermatitis, Marjolin’s ulcers, squamous cell carcinoma), positive pressure areas from a poor socket fit, bony nociceptive pain, adventitial bursitis, and neuroma formation. Neuromas may form as early 6-10 weeks after nerve transection and are thought to produce ectopic neural discharges resulting in severe residual limb pain. A diagnostic block can help isolate a neuroma as the source of pain.

Evidence suggests that RLP and PLP commonly co-occur, and patients may struggle to differentiate these pain types. Risk factors for these painful conditions include female sex, pre-amputation pain, longer duration of time since amputation, residual pain in the still-intact contralateral limb, and upper extremity amputation.

Current treatments of PLP and RLP are often inadequate for controlling patients’ symptoms. In addition to significant pain and disability, individuals with PLP and RLP also experience a higher incidence of indecisiveness, suicidal ideation, and thoughts of self-harm compared to pain-free health survey participants. Treatments include pre-operative analgesia, mirror therapy, guided motor imagery, acupuncture, medications such as tricyclic antidepressants (TCAs), selective serotonin reuptake inhibitors (SSRIs), gabapentinoids, sodium channel blockers, ketamine, opioids, and non-steroidal anti-inflammatories drugs (NSAIDs), transcranial magnetic stimulation, radiofrequency neurotomy, cryoablation, and neuromodulation (deep brain stimulation, dorsal root ganglion stimulation, spinal cord stimulation and percutaneous peripheral nerve stimulation). Additionally, various agents have been injected into and/or in close proximity to neuromas in attempt to mitigate pain symptoms, including local anesthetic, phenol, alcohol, and botulinum toxin. In general, these treatments have been associated with modest outcomes at best.

Pain improvement following mirror therapy suggests that the contralateral (intact) limb has an important role in PLP, and possibly RLP, resolution. This was further demonstrated in a randomized control trial that compared anesthetic and saline trigger point injections in participants’ intact limb (contralateral to the residual limb that experienced PLP). Contralateral

STU#:

limb anesthetic trigger points provided greater pain relief than placebo, supporting the exploration of contralateral limb interventions to reduce PLP. An animal study established the pathophysiologic basis for this via the crossed-withdraw reflex.

The crossed-withdraw reflex occurs when an individual withdraws a limb with an injured nerve after a stimulus is applied to the contralaterally equivalent healthy nerve (i.e., right and left median nerve). Animal studies have proposed the following reflex mechanism: activated dorsal horn neurons on the uninjured side either directly, or indirectly, activate ventral horn neurons on the injured side. This phenomenon occurs within 2 weeks of nerve injury and is likely due to plastic changes in the spinal cord. Furthermore, it appears that an injured nerve generates a greater proportion of wide-dynamic range (WDR) neuron activation on the contralateral limb nerve, when compared to contralateral WDR activation with two intact limb nerves. This forms the basis for the current understanding of central nervous system changes following amputation that may contribute to PLP/RLP.

While studies have evaluated ipsilateral sciatic nerve block for PLP, myofascial injections in the contralateral (intact) limb, and transcutaneous electric nerve stimulation (TENS) in the contralateral limb, no study to date has evaluated the efficacy of contralateral limb sciatic nerve block for the treatment of PLP/RLP. The present study aims to define the attributable effects of contralateral sciatic nerve block on pain and function in participants with post-amputation PLP/RLP.

We hypothesize that contralateral sciatic nerve block with 2% lidocaine will demonstrate superior clinical pain outcomes compared to sham in PLP/RLP. If this hypothesis proves correct, the study findings would fundamentally change the limb loss pain treatment paradigm. This would allow clinical teams to pursue more advanced contralateral procedures including perineural steroid injection and peripheral nerve stimulation. This could improve physical and psychological function, quality of life, and reduce overall healthcare utilization and cost in a substantial portion of the limb loss population.

We also believe that previous exploration into the basic science of the crossed-withdraw reflex and WDR neuron activity requires further validation with human subjects and clinical scenarios. A better understanding of this area will directly inform limb loss, pain, spinal cord, and neurology research.

## **STUDY ENDPOINTS:**

### Primary Outcome

Comparison of the proportions of participants reporting  $\geq 50\%$  improvement in NRS pain score from baseline at 15 minutes in treatment and sham groups

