### Secondary Outcomes (between and within-group comparisons will be used for each outcome):

- 1) Mean and standard deviation (SD) of change in NRS pain score at 1, 2, 3, 4, 5, 6, 24, 48, 72, 96, 120 hours post-saline and lidocaine injections
- 2) Mean and SD of average daily steps recorded at 24, 48, 72, 96, 120 hours post-saline and lidocaine injections (via Modus StepWatchTM or Evolution EvoWalkTM)

STU#:

- 3) Mean and SD of change in Orthotics and Prosthetics User's Survey (OPUS) score immediately post-injection and conclusion of washout (5 days) in saline and lidocaine groups
- 4) Mean and SD of change in Groningen Activity Restriction Scale (GARS) score immediately post-injection and conclusion of washout (5 days) in saline and lidocaine groups
- 5) General linear model analysis of the interaction between crossover sequence
- 6) Demographic factors associated with large improvement in NRS pain score
- 7) Complications associated with the procedures

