## POWER ANALYSIS

Power and sample size calculations for this clinical trial were performed based on the data from a small cross-over study (N = 8) by Casale et al. The primary outcome variable will be achievability of  $\geq 50\%$  pain relief (dichotomous variable with yes/no), calculated from pre- and post-inject NRS in each of the lidocaine and sham conditions (i.e., pre-injection NRS – post-injection NRS). Based on the data from Casale et al., along with our expected, overall success rate of 75% by lidocaine injection, we calculated the difference in two proportions of discordant pairs to be 0.625 and the overall proportion of discordant pairs to be 0.875. Using these values and binomial enumeration (1,500 enumerations), along with an

STU#:

alpha level of 0.05, a power of 0.80, a two-sided t-test, and a dropout rate of 10%, the sample size was estimated as 20.

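### The primary 15-minute pain score is analysed only as a 50% yes/no cut; a paired full-scale comparison at 15 minutes should be named as the first-ranked secondary outcome

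*Combined protocol and SAP*

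**What the plan says.** Under Primary Outcome, the endpoint is a "Comparison of the proportions of participants reporting" a drop of at least half in NRS at 15 minutes, lidocaine against sham. Objectives makes the same cut part of the hypothesis: the block "provides immediate clinically meaningful pain reduction, defined as the proportion of patients with at least 50% improvement in NRS pain score". The Power Analysis sizes the trial on "pain relief (dichotomous variable with yes/no), calculated from pre- and post-inject NRS in each of the lidocaine and sham conditions".

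Secondary outcome 1 is the full-scale measure: "change in NRS pain score at 1, 2, 3, 4, 5, 6, 24, 48, 72, 96, 120 hours post-saline and lidocaine injections". It has no 15-minute entry.

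In the Statistical Plan, the primary-outcome paragraph goes on to a test of average change in pain score, by unpaired t test or Mann-Whitney. It states no time and points to no listed outcome.

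The Visit 2 and Visit 3 procedures collect an NRS score before each injection and start the pain log 15 minutes after it. Every participant receives both injections. Both full-scale scores will therefore exist under both conditions.

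**The concern.** A yes/no cut ignores differences on either side of it. A participant going from 8 to 5 (3/8 = 37.5%) counts the same as one who does not change. One going from 8 to 4 (50%) counts the same as one who becomes pain free. With about 18 evaluable pairs that loss can matter.

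Interpretation is also at stake. If the responder test is not significant, the natural next question is whether average pain moved at 15 minutes. No listed outcome answers it. The one sentence that might do so leaves the time point open and discards the pairing. The Objectives also aim to define the relief attributable to the block, and a responder proportion does not show how much relief was obtained.

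**Working it through.** **Inputs, all from the Power Analysis:** "expected, overall success rate of 75% by lidocaine injection"; "the difference in two proportions of discordant pairs to be 0.625"; "the overall proportion of discordant pairs to be 0.875"; two-sided alpha 0.05; power 0.80; dropout 10%; N = 20.

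**Step 1: cells.** Lidocaine-only responders: (0.875 + 0.625)/2 = 0.75. Saline-only responders: (0.875 - 0.625)/2 = 0.125. Lidocaine success is also 0.75, so the both-responder cell is 0.75 - 0.75 = 0, and the saline rate is 0.125.

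**Step 2: reproduce N.** The section names a t-test, but these are McNemar inputs. Exact two-sided McNemar power is the sum over m of Bin(m; n, 0.875) times the probability that the exact binomial test on m discordant pairs gives p ≤ 0.05 when the lidocaine share is 0.75/0.875. Results: n = 17, 0.790; n = 18, 0.830; n = 20, 0.879. The smallest n reaching 0.80 is 18, and 18/0.9 = 20. The plan's figure reproduces.

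**Step 3: full-scale comparison.** The plan gives no NRS mean or SD, so a model must be assumed: percent improvement under the two conditions is bivariate normal with equal SDs and correlation ρ, cut to give 75% and 12.5% responders. The mean difference in SD units is z(0.75) - z(0.125) = 0.6745 + 1.1503 = 1.825. The paired effect is d = 1.825/√(2(1 - ρ)). Paired t power uses the noncentral t with n - 1 df and noncentrality d√n.

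The empty both-responder cell corresponds to ρ of about -1, giving d = 1.825/2 = 0.912. For other ρ, the response rates are held and the discordant cells follow from the model. With 18 pairs:

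| ρ | discordant cells | exact McNemar | paired t | gain (points) |
|---|---|---|---|---|
| -1 | 0.750 / 0.125 | 0.830 | 0.954 | 12.4 |
| -0.5 | 0.696 / 0.071 | 0.896 | 0.988 | 9.2 |
| 0 | 0.656 / 0.031 | 0.958 | 0.999 | 4.1 |
| 0.5 | 0.631 / 0.006 | 0.991 | about 1.00 | 0.9 |

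**Step 4: how much is due to the cut.** At ρ = -1 and 18 pairs, mid-p McNemar has power 0.887, so the gain is 0.954 - 0.887, about 7 points. With all 20 pairs and the exact test it is 0.972 - 0.879, about 9 points.

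**Step 5: weaker lidocaine response.** These rates are illustrative and not from the documents. Saline stays at 12.5%, with 18 pairs, exact McNemar v paired t:

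| lidocaine rate | ρ = -1 | ρ = 0 | ρ = 0.5 |
|---|---|---|---|
| 60% | 0.601 v 0.801 | 0.765 v 0.977 | 0.874 v about 1.00 |
| 50% | 0.425 v 0.633 | 0.538 v 0.902 | 0.645 v 0.996 |

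The gains run from about 13 points (60%, ρ = 0.5) to about 36 (50%, ρ = 0).

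**Step 6: check on real score values.** Simulated whole-number 0-10 scores (assumed baseline 5 to 10, SD of improvement 20 to 40 percentage points), tested as raw NRS differences at ρ = -1 with 18 pairs, gave McNemar 0.81 to 0.84 and paired t 0.94 to 0.96. The gain was 11 to 12 points, and about 11 with the signed-rank test. The result does not depend on unbounded or continuous scores.

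**The case against.** The strongest reply is that the responder rate is the question the trial asks. Objectives defines the hypothesis by the 50% threshold, and Background ties success to offering patients further contralateral procedures, which is a question about individual response. The absence of a cited guideline for the cut is not an error. This stands, and it is why the primary endpoint should stay. A reader might infer that the full-scale score ought to replace it. That would change the stated hypothesis, and the plan has no NRS SD on which to size the new test.

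A reader might also infer that the trial is underpowered, or that the plan's own inputs show a 12-point loss. Neither follows. Exact McNemar power at those inputs is 0.83 against a target of 0.80. The 12 points need the added normal model and a correlation of about -1, which means that those who do best on lidocaine do worst on saline. That is an odd pattern within one person, and it comes from an empty cell in inputs drawn partly from an eight-person study. At 75% v 12.5% it is the largest gain of the correlations examined, not a floor.

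Finally, the Statistical Plan's sentence on average change follows one about immediate relief and can be read as meaning 15 minutes. It would be wrong to say that no full-scale analysis is planned. But the reader has to supply the time point, and the test named is unpaired.

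**Conclusion.** The point holds as a cheap improvement in efficiency and interpretability. No listed outcome compares full-scale NRS at 15 minutes, and the one sentence that comes close lacks a time point, a listed outcome and a paired test.

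At the plan's response rates the gain in power from a paired full-scale test is between about 1 and 12 points, depending on a correlation that the documents do not give. It matters more if the block works less well than expected. The 75% is the team's own expectation, and Background says that no study has yet evaluated this block.

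All gains rest on the bivariate normal, equal-SD assumption. The 0.83 for the responder test assumes an exact paired analysis, which the sample-size inputs imply but the Statistical Plan does not name.

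**What to change.** - **Primary Outcome:** keep the ≥50% responder proportion.
- **Secondary outcome 1:** add 15 minutes. Name the within-participant lidocaine-minus-saline difference in NRS change, from pre-injection to 15 minutes, as the first-ranked secondary outcome. Report the estimate and 95% CI beside the primary result, whatever that result is.
- **Statistical Plan:** tie the average change in pain score to 15 minutes. Replace the unpaired test with a within-participant analysis: a paired t or signed-rank test, or a crossover model with a period term.

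The cost is wording in two sections and one more secondary comparison. No new data, visits or participants are needed, because both scores are already collected around each injection.

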### Secondary Outcomes (between and within-group comparisons will be used for each outcome):

- 1) Mean and standard deviation (SD) of change in NRS pain score at 1, 2, 3, 4, 5, 6, 24, 48, 72, 96, 120 hours post-saline and lidocaine injections
- 2) Mean and SD of average daily steps recorded at 24, 48, 72, 96, 120 hours post-saline and lidocaine injections (via Modus StepWatchTM or Evolution EvoWalkTM)

STU#:

- 3) Mean and SD of change in Orthotics and Prosthetics User's Survey (OPUS) score immediately post-injection and conclusion of washout (5 days) in saline and lidocaine groups
- 4) Mean and SD of change in Groningen Activity Restriction Scale (GARS) score immediately post-injection and conclusion of washout (5 days) in saline and lidocaine groups
- 5) General linear model analysis of the interaction between crossover sequence
- 6) Demographic factors associated with large improvement in NRS pain score
- 7) Complications associated with the procedures

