### *Visit 2 (procedure 1)– Randomization and Study Intervention*

STU#:

Eligible participants will return to the Lavin 14th floor Pain clinic within 2 weeks of the initial visit. Participants will be randomized to treatment or sham group. Participant pre-procedure 1 NRS pain score will be collected. Individual pain log will start 15 minutes after procedure. Participant will log pain score every hour until asleep. The next day, participant will record daily NRS pain score for 5 days.

Randomization

A computer-generated 1:1 block randomization scheme (<https://www.randomizer.org>) will be used to assign participants to receive a peri-sciatic nerve injection with either 10 mL of 2% lidocaine or 10 mL of preservative-free saline (compounded by the 11th floor Lavin pharmacy and labeled with a “1” or “2” to ensure adequate blinding). Randomization will be performed by a research assistant by opening an opaque envelope to reveal the participant number and group assignment printed inside of the envelope. This will instruct authorized study personnel to draw up either 2% lidocaine or saline (labeled “1” or “2” by compounding pharmacy per above). The blinded injectionist will be provided an unlabeled syringe of injectate immediately before the injection procedure. Participants, injectionist, and study personnel who collect outcomes data will be blinded to group assignment.

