Eligible participants will return to the Lavin 14th floor Pain clinic within 5 days of visit 2. Participant pre-procedure 2 NRS and OPUS will be collected. Note that this will serve as post-procedure 1 washout and pre-procedure 2 intervention data point.

Both groups: will cross over and undergo treatment as described in *Visit 2*. Participant pain log will start 15 minutes after procedure 2. Participant will log pain scores every hour until asleep. The next day, participant will record daily NRS pain score for 5 days.

*Telephone call 1,2,3:* participant will be called at 1- and 5-days post-procedures for NRS, OPUS survey and safety monitoring by research coordinator (see Safety Monitoring below).

**SAFETY MONITORING** Participants will be contacted one day following both interventions to assess for any adverse events or side effects.

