#### STATISTICAL PLAN

Data for the primary outcome variable, proportion of participants reporting  $\geq 50\%$  immediate pain reduction from baseline, will be reported as the mean and standard deviation (or median and interquartile range if not normally distributed) of the lidocaine and sham groups. Mean change in pain score, will be examined using an unpaired t test (NCSS) (or Mann-Whitney U test if not normally distributed). The median difference and its 95% CI will be calculated. The criterion for rejection of the null hypothesis will be  $P < 0.05$ .

Participant data and secondary variables that are characterized by nominal data will be summarized as the number of participants in each category and the percentage of all participants in the group that they represent. These variables will be compared between the groups using the Pearson  $\chi^2$  test, or when at least one of the cells of the contingency table had an expected number less than five, the Fischer exact probability test. The Miettinen-Nurminen score will be used to calculate 95% CIs for differences in percentages where indicated.

Variables that are characterized by ordinal data and non-normally distributed continuous data (e.g., procedure time) will be summarized as median and interquartile range. These variables will be compared between the groups using the Mann-Whitney U test. Median differences and their 95% CIs will be calculated where indicated.

Variables that are characterized by normally distributed continuous data (e.g., age and body weight) will be summarized as mean and standard deviation. These variables will be compared between the groups using the unpaired t test (NCSS). Mean differences and their 95% CIs will be determined.

In case there were significant differences in the demographic variables, multivariate logistic and linear regression analyzes will be conducted to examine the binary and continuous outcome variables by group, while accounting for the statistically significant demographic variables analysis will be used to determine if any demographic or clinical variables (age, BMI, duration of pain, etc.) are independently associated with successful pain (NRS) outcomes.

Lastly, Pearson's correlation coefficients will be computed to assess the relationships among various demographic and procedural covariates.

STU#:

STU#:

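### The secondary NRS outcome is analysed as raw change, without the pre-injection score or period as model terms, which probably costs precision at no gain

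*Combined protocol and SAP*

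**What the plan says.** Under Study Endpoints, Secondary Outcomes item 1 is "Mean and standard deviation (SD) of change in NRS pain score" at eleven time points from 1 to 120 hours after each injection. The item does not say which baseline the change is measured from.

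The Statistical Plan tests mean change in pain score with an unpaired t test, or a Mann-Whitney U test if the data are not normal. Neither test has a covariate, a period term or a participant term.

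The data for an adjustment exist. At Visit 2, "Participant pre-procedure 1 NRS pain score will be collected"; at Visit 3, "Participant pre-procedure 2 NRS and OPUS will be collected". The Visit 3 text adds that this second score also serves as the end-of-washout value for procedure 1.

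Two other places touch on modelling. The Statistical Plan opens its only regression adjustment with "In case there were significant differences in the demographic variables". Secondary Outcomes item 5 names a general linear model of an interaction involving crossover sequence, but the sentence does not name the other term, and the Statistical Plan does not mention the model.

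**The concern.** Subtracting a baseline fixes its slope at 1. A single-item score taken just before an injection is noisy. If it tracks the later score only moderately within a person, subtraction adds noise to the treatment comparison, whereas a fitted slope uses only the information the baseline carries. A shift between periods that affects post-injection but not pre-injection scores also stays in the error term when period is not modelled.

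Neither existing provision supplies the adjustment. Every participant receives both injections, so fixed demographics cannot differ between lidocaine and saline except through dropout; the regression also names neither pre-injection NRS nor period. Item 5 as worded names neither term either.

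At stake is the width of the intervals for how long any pain effect lasts after the 15-minute primary assessment, in a trial with about 18 evaluable participants.

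**Working it through.** **The plan's own figure.** The Power Analysis gives the "difference in two proportions of discordant pairs to be 0.625", a total discordant proportion of 0.875, two-sided alpha 0.05 and "a power of 0.80". The discordant cells are therefore (0.875 + 0.625)/2 = 0.75 and (0.875 − 0.625)/2 = 0.125. Exact two-sided McNemar power is 0.790 with 17 pairs and 0.830 with 18. Allowing 10% dropout, 18/0.9 = 20. N = 20 is reproduced. It rests on the binary primary, so nothing below changes it.

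**Assumptions, none of them in the documents.** NRS SD 2, equal at all occasions; pre-post correlation within a period rw; one common correlation between periods rb; 18 completers, 9 per sequence. The correlation of pre- and post-injection scores after removing the person's own level is r = (rw − rb)/(1 − rb).

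**Against a paired analysis of raw change.** Let s² be the within-person variance. The variance of one participant's lidocaine-minus-saline difference is:

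- raw change: 2s² + 2s² − 4rs² = 4s²(1 − r)
- post-injection score only: 2s²
- adjusted for the pre-injection score: 2s²(1 − r²)

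Adjusted over raw change is (1 + r)/2. Post-only over raw change is 1/(2(1 − r)), which is below 1 whenever r < 0.5; there, raw change is less precise than ignoring the baseline.

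Estimating the slope multiplies the adjusted variance by about 1 + 1/(18 − 4) = 1.071. The residual degrees of freedom fall from 17 to 15, so the t multiplier rises from 2.110 to 2.131 (ratio 1.010). CI-width ratio ≈ √(variance ratio) × 1.010.

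| r | (1 + r)/2 | × 1.071 | Simulated variance ratio | CI-width ratio |
|---|---|---|---|---|
| 0 | 0.50 | 0.54 | 0.52 | 0.74 |
| 0.2 | 0.60 | 0.64 | 0.64 | 0.81 |
| 0.4 | 0.70 | 0.75 | 0.74 | 0.87 |
| 0.6 | 0.80 | 0.86 | 0.85 to 0.87 | 0.93 |
| 0.8 | 0.90 | 0.96 | – | 0.99 |
| 0.9 | 0.95 | 1.02 | – | 1.02 |

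**Against the planned unpaired t test.** That test has 36 − 2 = 34 degrees of freedom (multiplier 2.032). With one common between-period correlation, a person's two change scores are uncorrelated (rb − rb − rb + rb = 0), so pairing alone recovers nothing. Simulated ratios of adjusted to planned CI width:

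| rw, rb | No period effect | 1-point period effect |
|---|---|---|
| 0.5, 0.5 | 0.76 | 0.74 |
| 0.7, 0.7 | 0.76 | 0.72 |
| 0.7, 0.5 | 0.90 | 0.85 |
| 0.8, 0.5 | 0.96 | 0.89 |
| 0.9, 0.3 to 0.5 | 1.02 to 1.04 | 0.88 to 0.90 |

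Check at rw = 0.7, rb = 0.5: √(0.70 × 1.071) × 2.131/2.032 = 0.91, close to the simulated 0.90. The period effect here is a shift in the period-2 post-injection score only; a shift common to pre and post would cancel in the change.

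**Power for an assumed 1.5-point difference, no period effect.** At rw = rb = 0.5: 0.59 planned, 0.82 adjusted. At rw = 0.7, rb = 0.5: 0.80 planned, 0.78 paired on raw change, 0.88 adjusted.

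**Period and balance.** With balanced sequences and a 1-point period effect, the planned test is conservative (null rejection 0.022 to 0.042 instead of 0.05), not biased. With 10 and 8 completers, the unadjusted contrast is off by 1 × (10 − 8)/18 = 0.11 NRS points and the adjusted one by about 0.

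**The case against.** The strongest reply is that change score versus covariate adjustment is an efficiency choice whose benefit depends on an unknown correlation. Six of the eleven time points fall within 6 hours of the covariate, where the correlation could be high. That stands: at r about 0.8 with no period effect there is nothing to gain, and at 0.9 the adjusted interval is slightly wider. A reader might infer that the planned intervals are always wider than necessary; the documents do not support that.

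A reader might also infer that the plan ignores period altogether. Item 5 prevents so flat a statement. If its missing term is treatment, then in a two-sequence, two-period crossover the treatment-by-sequence interaction is the period effect. But the item is unfinished and is not carried into the analysis, so it yields no period-adjusted treatment estimate.

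It is likewise tempting to say that the plan subtracts each period's own pre-injection score. Item 1 does not say so, and baseline measures are also taken at Visit 1.

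Finally, the adjustment is not free of assumptions. The period-2 covariate is the day-5 post-washout score; if the first injection still acts then, that covariate is affected by treatment. Raw change from the same score has the same weakness, so this calls for a sensitivity analysis and does not favour the current plan.

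**Conclusion.** The point holds as a loss of efficiency in one secondary outcome. Over the assumed correlations, with 18 completers, the adjusted interval runs from about 24% narrower to 4% wider than planned without a period effect, and is 10% to 28% narrower with an assumed 1-point period effect. The possible gain is much larger than the possible cost, but its actual size cannot be known from the documents.

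A reader might infer that the trial's main result or its sample size is compromised. Neither follows: the primary is a responder proportion, N = 20 is reproduced, and with balanced sequences and no carryover the planned contrast is unbiased. The 0.11-point bias needs both an assumed 1-point period effect and unequal completion, and it is small on the NRS.

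**What to change.** In the Statistical Plan:

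- State that change is measured from that period's own pre-injection NRS.
- Analyse post-injection NRS with a linear mixed model. Fixed effects: treatment, period, the period's pre-injection NRS and the participant's mean pre-injection NRS. Random effect: participant. Equivalently, at each time point, regress the paired post-injection difference on the paired pre-injection difference and sequence.
- Report the adjusted lidocaine-minus-saline difference with its 95% CI. Keep raw mean (SD) change as description.
- Complete item 5 as a named term within this model.
- Report a sensitivity analysis of post-injection scores without the baseline covariate, because the period-2 covariate relies on there being no carryover into day 5.
- Treat 120 hours separately, since the period-1 outcome there may be the same score as the period-2 covariate.
- Say what replaces the Mann-Whitney fallback if residuals are clearly non-normal.

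The cost is wording and about two degrees of freedom out of 17, or a few percent of interval width if r is very high. No new visits, participants or measurements are needed.
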